Pharmacokinetics and Safety of Remdesivir for Treatment of COVID-19 in Pregnant and Non-Pregnant Women in the United States

IND#154,388 DAIDS study ID # 38746

This file contains the current IMPAACT 2032 protocol, which is comprised of the following documents, presented in reverse chronological order:

- Corrected Clarification Memorandum #2, dated 21July 2021
- Clarification Memorandum #1, dated 12 April 2021
- Protocol Version 2.0, dated 18 December 2020

Corrected Clarification Memorandum #2 for:

IMPAACT 2032

Pharmacokinetics and Safety of Remdesivir for Treatment of COVID-19 in Pregnant and Non-Pregnant Women in the United States

Version 2.0, dated 18 December 2020

DAIDS Study ID #38746 IND # 154388

Corrected Clarification Memorandum Date: 21 July 2021

Summary of Clarifications and Rationale

This is a corrected version of Clarification Memorandum (CM) #2, which clarifies pharmacokinetic (PK) specimen collection procedures for participants who discontinue remdesivir (RDV) after initial PK sampling. This CM also updates the Protocol Team Roster. The corrected version of CM#2 replaces the original clarification memorandum, which should be disregarded.

Implementation

This CM will be submitted to the Johns Hopkins Medicine Institutional Review Board, which serves as the single Institutional Review Board (sIRB) for IMPAACT 2032, for their information; however, approval of this CM is not required by the study sponsor prior to implementation. Sites may submit this CM to their local IRBs/ECs for their information or, if required by the local IRBs/ECs, for their approval prior to implementation. This CM and any applicable IRB/EC correspondence should also be filed in essential document files for IMPAACT 2032.

The information included in this memorandum will be incorporated into the next protocol amendment.

- 1. Section 6.7 Early Discontinuation of Remdesivir of the IMPAACT 2032 protocol specifies that participants who initiate RDV and undergo PK sampling and then discontinue RDV prior to the 5th infusion will have no further PK sampling. This memorandum clarifies that PK sampling includes intensive PK, intracellular PK, protein binding plasma, or single PK plasma (48-hour post-last infusion data collection timepoint) sampling.
- 2. To reflect current membership, [name] is removed from the Protocol Team Roster and [name] is added as a protocol laboratory data manager, as shown below.

[name], BS Frontier Science Foundation [name]

[contact] [name] Email: [contact]

Clarification Memorandum #1 for:

IMPAACT 2032

Pharmacokinetics and Safety of Remdesivir for Treatment of COVID-19 in Pregnant and Non-Pregnant Women in the United States

Version 2.0, dated 18 December 2020

DAIDS Study ID #38746 IND # 154388

Clarification Memorandum Date: 12 April 2021

Summary of Clarifications and Rationale

This Clarification Memorandum (CM) updates protocol specifications to reflect current policies of the Division of AIDS (DAIDS), National Institute of Allergy and Infectious Diseases (NIAID), and National Institutes of Health (NIH). It also updates the wording related to the IMPAACT Network Certificate of Confidentiality and adds the protocol IND number. These updates do not impact the study design or study-specific procedures.

Implementation

This CM will be submitted to the Johns Hopkins Medicine Institutional Review Board, which serves as the single Institutional Review Board (sIRB) for IMPAACT 2032, for their information; however, approval of this CM is not required by the study sponsor prior to implementation. Sites may submit this CM to their local IRBs/ECs for their information or, if required by the local IRBs/ECs, for their approval prior to implementation.

IRBs/ECs may have acknowledged and/or approved remote site monitoring strategies prior to the issuance of this CM. If so, sites should file documentation of this acknowledgement and/or approval in their essential document files for IMPAACT 2032. This CM and any applicable IRB/EC correspondence should also be filed in essential document files for IMPAACT 2032.

The information included in this memorandum will be incorporated into the next protocol amendment.

A. DAIDS Policy Updates

1. Protocol Section 12 is updated to reflect current DAIDS policies for clinical site monitoring, which allow for on-site and remote monitoring. The prior contents of this section are replaced with the following:

Under contract to DAIDS or NICHD, site monitors will inspect study site facilities and review participant study records — including informed consent forms, paper-based CRFs (if used), eCRFs, medical records, laboratory records, and pharmacy records — to ensure protection of study participants, compliance with the sIRB approved protocol, and accuracy and

completeness of records. Monitors also will review essential document files to ensure compliance with all applicable regulatory requirements. Site investigators will make study facilities and documents available for inspection by monitors.

Monitoring visits may be conducted on-site or remotely. Remote visits may include remote source document verification using methods specified for this purpose by DAIDS or NICHD. Remote monitoring visits may be performed in place of, or in addition to, onsite visits to ensure the safety of study participants and data integrity (1). Site investigators will make study documents available for site monitors to review utilizing a secure platform that is 21 CFR Part 11 and HIPAA compliant. Potential platform options include: Veeva SiteVault, Medidata Rave Imaging Solution, Medidata Remote Source Review, site-controlled SharePoint or cloud-based portal, and direct access to electronic medical records. Other secure platforms that are 21 CFR Part 11 and HIPAA compliant may be utilized, as allowed by DAIDS or NICHD.

Reference:

- 1. FDA Guidance on Conduct of Clinical Trials of Medical Products During the COVID-19 Public Health Emergency: Guidance for Industry, Investigators, and Institutional Review Boards, March 2020, Updated on January 27, 2021. Accessed at: https://www.fda.gov/media/136238/download
- 2. Protocol Section 14.5 refers to the DAIDS policy on identification and classification of critical events. This policy has been retired. Section 14.5 is removed from the protocol and Section 13.1 has been updated to refer to the reporting requirements that still apply for sites conducting this study. In Section 13.1 no changes are made to the first paragraph and the prior contents of the second paragraph are replaced with the following:
 - Prior to study initiation, site investigators must obtain sIRB review and approval of this protocol and site-specific informed consent forms in accordance with 45 CFR 46; subsequent to initial review and approval, the sIRB must review the study at least annually. Site investigators must promptly report to the sIRB any changes in the study and must comply with the requirements of 45 CFR 46.108(a)(4) and 21 CFR 56.108(b) for promptly reporting the following: unanticipated problems involving risks to participants or others; serious or continuing noncompliance with applicable regulations or the requirements or determinations of the sIRB; and any suspension or termination of sIRB approval.
- 3. Protocol Section 14.6 (now re-numbered as Section 14.5) refers to requirements for entry of study results into ClinicalTrials.gov. To reflect current NIH and regulatory requirements, the prior contents of this section are replaced with the following:
 - The NIH Policy on Dissemination of NIH-funded Clinical Trial Information establishes the expectation that clinical trials funded in whole or in part by the NIH will be registered and have summary results information submitted to ClinicalTrials.gov for public posting. The protocol team will comply with this policy as well as the requirements of 42 CFR 11.
- 4. Protocol Sections 11.1, 11.2, 11.3, 13.7, 14.3, and 14.4 refer to the following DAIDS policies:
 - Requirements for Essential Documents at Clinical Research Sites Conducting DAIDS Funded and/or Sponsored Clinical Trials
 - Requirements for Source Documentation in DAIDS Funded and/or Sponsored Clinical Trials
 - Requirements for Clinical Quality Management Plans

• Requirements for Manual of Operational Procedures

These policies have been retired and replaced with instructions for sites that are now contained in the DAIDS Site Clinical Operations and Research Essentials (SCORE) Manual. Throughout the protocol, references to the above-listed policies are replaced with requirements specified in the DAIDS SCORE Manual (edits not shown here). The SCORE Manual is available at: https://www.niaid.nih.gov/research/daids-clinical-site-implementation-operations

B. Certificate of Confidentiality

The Certificate of Confidentiality described in protocol Section 13.7 has been deemed issued to the IMPAACT Network effective with the start date of the current Network funding cycle (1 December 2020). The first sentence in the last paragraph of this section is replaced with the following:

In addition to the above, a Certificate of Confidentiality has been deemed issued for the IMPAACT Network by the US Department of Health and Human Services.

C. Protocol Cover Page

The IND Number # 154388 is added to the cover page

Pharmacokinetics and Safety of Remdesivir for Treatment of COVID-19 in Pregnant and Non-Pregnant Women in the United States

A Study of the International Maternal Pediatric Adolescent AIDS Clinical Trials Network

Sponsored by:

National Institute of Allergy and Infectious Diseases

Eunice Kennedy Shriver

National Institute of Child Health and Human Development

National Institute of Mental Health

Support Provided by:

Gilead Sciences, Inc.

Name of Investigator of Record (printed)	

Pharmacokinetics and Safety of Remdesivir for Treatment of COVID-19 in Pregnant and Non-Pregnant Women in the United States

ABBREVIATIONS AND ACRONYMS

AAG α1-acid glycoprotein

AE adverse event

ALT alanine transaminase
AST aspartate aminotransferase
ATP adenosine triphosphate
AUC area under the curve
CBC complete blood count

CDC Centers for Disease Control and Prevention

CFR Code of Federal Regulations

CI confidence interval

CMC Clinical Management Committee COVID-19 coronavirus disease of 2019

CRP C-reactive protein
CV coefficient of variation
DAIDS Division of AIDS
DBS dried blood spots

DMC Data Management Center EAE expedited adverse event

ECMO extracorporeal membrane oxygenation

EUA Emergency Use Authorization

EC ethics committee ECG electrocardiogram

ESR erythrocyte sedimentation rate
eCRF electronic case report form
eGFR estimated glomerular filtration rate
EMA European Medical Association

EMA European Medical Association FDA Food and Drug Administration

FDAAA United States Food and Drug Administration Amendments Act of 2007

GCP good clinical practices GFR glomerular filtration rate GMR geometric mean ratio

GS-5734TM remdesivir

GS-441524 remdesivir dephosphorylated nucleoside analog

GS-443902 remdesivir active triphosphate form human immunodeficiency virus

hs high sensitivity ICU intensive care unit

IMPAACT International Maternal Pediatric Adolescent AIDS Clinical Trials Network

IRB institutional review board IND investigational new drug INR international normalized ratio

IoR Investigator of Record

IV intravenous

LAR legally authorized representative

LDH lactate dehydrogenase

LDMS laboratory data management system

LPC laboratory processing chart

MERS-CoV Middle East respiratory syndrome

MMWR Morbidity and Mortality Weekly Report CDC

MOG Management Oversight Group

MOP manual of procedures

NCA non-compartmental pharmacokinetic analysis
NIAID National Institute of Allergy and Infectious Diseases

NICHD National Institute of Child Health and Human Development

NIH National Institutes of Health

OHRP Office for Human Research Protection PBMCs peripheral blood mononuclear cells

PCD primary completion date

PID participant identification number

PK pharmacokinetic

PRO Protocol Registration Office

PT prothrombin time

PTT partial thromboplastin time

RDV remdesivir

RSC Regulatory Support Center SAE serious adverse event

Email: [contact]

Site 5127, Pediatric Perinatal HIV Clinical Trials Unit

Pediatric/Perinatal HIV Clinical Trials Unit [name] USA

[name] Investigator of Record [contact]

Email: [contact]

[name], FMD, CCRP Study Coordinator [contact]

Email: [contact]

Site 5128, Texas Children's Hospital CRS

Baylor / Texas Children's Hospital [name] USA

[name] Investigator of Record [contact] Email: [contact] [name], MSN, RN, CPN

Study Coordinator [contact]

email: [contact]

Site 5129, University of Puerto Rico Pediatric HIV/AIDS Research Program CRS

University of Puerto Rico Pediatric HIV/AIDS Research site [name] USA Pediatric HIV/AIDS Research site

[name] Investigator of Record [contact] Email: [contact]

[name], MS Study Coordinator [contact]

Email: [contact]

Site 6501, St. Jude Children's Research Hospital CRS

St. Jude Children's Research Hospital [name] USA

[name] Investigator of Record [contact]

Email: [contact]

[name], APRN-BC

Study Coordinator [contact] Email: [contact]

Pharmacokinetics and Safety of Remdesivir for Treatment of COVID-19 in Pregnant and Non-Pregnant Women in the United States

SCHEMA

Purpose: To describe the pharmacokinetic (PK) properties and safety of

remdesivir (GS-5734TM) (RDV) administered to pregnant and non-

pregnant women with COVID-19.

Design: Phase IV, prospective, open label, non-randomized opportunistic PK

study

Study Population: Pregnant and non-pregnant women of childbearing potential hospitalized

and receiving RDV for treatment of COVID-19.

Sample Size: Arm 1: Target enrollment of 20 pregnant women with evaluable PK data

Arm 2: Target enrollment of 20 non-pregnant women of childbearing

potential with evaluable PK data

Drug under study: RDV will not be provided as part of the study. Participants will be

administered RDV intravenously once daily for up to 10 days per clinical

care.

Study Duration: Approximately 15 months total. Accrual is expected to be completed

within approximately 6 months from first enrollment. Enrolled women in Arm 1 will be followed for 4 weeks after the last RDV infusion or through delivery, whichever comes later. Enrolled women in Arm 2 will

be followed for 4 weeks after the last RDV infusion.

Primary Objectives

Arm 1:

- To describe the pharmacokinetics of RDV and its metabolite, GS-441524, after administration to pregnant women as part of clinical care.
- To describe the clinical and laboratory safety outcomes through four weeks post-last infusion and during delivery in pregnant women receiving RDV as part of clinical care.

Secondary Objectives

Arm 2:

- To describe the pharmacokinetics of RDV and its metabolite, GS-441524, after administration to non-pregnant women of childbearing potential as part of clinical care.
- To describe the clinical and laboratory safety outcomes through four weeks post-last infusion in non-pregnant women of childbearing potential receiving RDV as part of clinical care.

Other Objectives

Arm 1:

• To describe RDV placenta transfer with collection of plasma and cord blood samples at delivery in mothers who have received a dose of RDV within the preceding 5 days.

Arms 1 and 2:

- To compare the pharmacokinetics of RDV and its metabolite, GS-441524, in pregnant women to those observed in non-pregnant women of childbearing potential.
- To describe and compare intracellular concentrations of RDV's active intracellular nucleotide triphosphate (GS-443902) in pregnant and non-pregnant women of childbearing potential receiving RDV as part of clinical care.
- To develop a population PK (PopPK) model of RDV and its metabolites in pregnant and nonpregnant women receiving RDV and evaluate associations between clinical characteristics and RDV and GS-441524 pharmacokinetics.
- To assess plasma protein binding of RDV in pregnant women and non-pregnant women of childbearing potential.
- To describe the frequency of detection in breast milk and the relative concentrations in breast milk and plasma of RDV and GS-441524 in lactating women undergoing RDV PK sampling.

Pharmacokinetics and Safety of Remdesivir for Treatment of COVID-19 in Pregnant and Non-Pregnant Women in the United States

Figure 1: Overview of Study Design

Arm 1

Pregnant Women Hospitalized with COVID-19

(Target 20 PK evaluable)

Arm 2

Non-Pregnant Women Hospitalized with COVID-19

(Target 20 PK evaluable)

Safety Evaluations: Clinical and Laboratory Data Collection (Chart Abstraction/Remote Visits)

- Intensive PK
 Sampling (3rd, 4th or 5th infusion)
- Breast milk collection (lactating women who consent only)
- Single PK Sampling (2nd – 5th infusions)*
 *Single PK sampling will not occur on day of intensive PK sampling

- Single PK Sampling (48-Hours only)*
- *only for women still hospitalized
- Breast Milk Collection (48-Hours only)*
- *lactating women still hospitalized who consent only

Single PK Sampling (maternal and cord blood)*

*(Only for pregnant women who received RDV within 5 days prior to delivery)

[^] Delivery visit may occur during infusions or safety follow-up.

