1 INTRODUCTION

1.1 Background

As of November 23, 2020, Centers for Disease Control and Prevention (CDC) received 12,175,921 COVID-19 case reports for the United States (U)S since January 22, 2020. There were slightly more women (52%) than men (48%) included in these reports (1). The most recent tracking data from CDC includes 39,857 case reports of US pregnant women with COVID-19 received between January 22 and November 23, 2020, with 53 deaths and 8,284 hospitalizations, although these data did not distinguish between hospitalization for COVID-19 conditions from admissions for pregnancy-related indications, such as delivery. The race/ethnicity breakdown of the pregnancy COVID-19 cases was 37% Hispanic, 35% White Non-Hispanic, 19% Black Non-Hispanic, 3%, Asian and 6% Multiple/Other (2). In an earlier MMWR publication describing the period between January 22 and June 7, 2020, CDC reported receiving notifications of 326,335 women of reproductive age (15-44 years) with positive SARS-CoV-2 test results. Of the 91,412 of these women with pregnancy data, 9% (8,207) were pregnant. Hospitalization was reported in 31.5% of pregnant women compared to 5.8% of nonpregnant women but the data did not distinguish between hospitalization for COVID-19 conditions from admissions for pregnancy-related indications, such as delivery. After adjusting for age, presence of underlying medical conditions, and race/ethnicity, pregnant women were significantly more likely to be hospitalized (aRR = 5.4, 95%) confidence interval [CI] = 5.1-5.6), to be admitted to the intensive care unit (ICU) (aRR = 1.5, 95% CI = 1.2–1.8) and to receive mechanical ventilation (aRR = 1.7, 95% CI = 1.2–2.4) than nonpregnant women (3). Increased need for intensive care during pregnancy has also been reported in Swedish women with COVID-19 (4). A review of published data on severe coronavirus infections in pregnancy reported adverse pregnancy outcomes, including maternal death, preterm delivery, stillbirth and neonatal death, as well as respiratory compromise requiring ICU care and mechanical ventilation, in pregnant women with COVID-19, although at lower frequency than with MERS-CoV and SARS-CoV-1 (5).

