4.1 Inclusion Criteria – Arm 1 (Pregnant Women)

Women must meet all of the following inclusion criteria to be enrolled in Arm 1.

4.1.1 Of legal age or otherwise able to provide independent informed consent as determined by site SOPs and consistent with all applicable IRB policies and procedures, and is willing and able to provide informed consent for her own participation in this study.

Or

Of legal age to provide independent informed consent but is unable to provide informed consent (e.g. impaired capacity, as determined by site SOPs and consistent with all applicable IRB policies and procedures) and a Legally Authorized Representative (LAR) is willing and able to provide written informed consent on behalf of the participant in accordance with 21 CFR 50.27.

Note: All sites must follow the policies and procedures of all applicable IRBs; this includes single IRB (sIRB) policies and procedures. Refer to Section 13.1 for more information on sIRB oversight.

- **4.1.2** At study entry, viable intra-uterine pregnancy of any gestational age, based on medical records.
- **4.1.3** At study entry, hospitalized AND has confirmed or suspected COVID-19, based on medical records.
- **4.1.4** At study entry, receiving or expected to receive RDV for COVID-19 clinical care, as prescribed by the clinical care provider and documented in medical records.

Note: The study investigator or designee will confirm that a potential study participant is receiving or expected to receive RDV based on information in the medical record.

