- **4.3.5** At study entry, has any other condition, that, in the opinion of the site investigator or designee, would make participation in the study unsafe, complicate interpretation of study outcome data, or otherwise interfere with achieving study objectives.

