6.3 Pre-infusion

The Pre-infusion period is defined as 48-hours priors to initiation of RDV infusions for COVID-19. Clinical and laboratory data will be collected per Table 2 for this time period (unless alternate time period is specified for specific data elements). If Screening/Entry occurs within or after 48-hours prior to the first RDV infusion, the clinical and laboratory data for the Pre-infusion period will be collected retrospectively after study entry.

Table 2: Data Collection Requirements for Pre-infusion Period

Evaluation	Enter into eCRFs or SES	
Medical History	 Record the following as available in the medical records: All medical conditions of any grade occurring or ongoing within 48 hours prior to the first infusion of RDV. These will be considered preexisting conditions and unrelated to RDV. Arm 1: Major obstetrical diagnoses during the current pregnancy prior to start of RDV infusions Arm 1: Gestational age at 48 hours prior to first infusion. Arm 1: Prior pregnancy information (number and dates of prior pregnancies, outcome of prior pregnancies) Last menstrual period 	

Evaluation	Enter into eCRFs or SES
	 Hospitalization for COVID-19 (COVID-19 status at hospitalization, COVID-19 symptoms onset date, hospitalization onset date, discharge date)
Concomitant Medications	Record the following medications available in the medical records EXCEPT RDV: • All prescription medications • Blood products and transfusions • All investigational drugs
Vital Signs	Record the following measurements that are available in the medical records: Record only once: Height Weight Record the most abnormal measurement in a 24-hour period: Highest systolic blood pressure Temperature Pulse rate Pulse oximetry
Respiratory Status	Record the respiratory and/or ventilation status

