7.2 Safety-Related Data Collection

The definition of the term adverse event provided in Version 2.0 of the Manual for Expedited Reporting of Adverse Events to DAIDS (DAIDS EAE Manual) will be used in this study. This definition will be applied to all participants, beginning at the time of the first infusion until 4 weeks after the last infusion (and for Arm 1 participants, during the Delivery period, if that occurs after Safety Follow-up period). Any untoward medical conditions occurring prior to the first infusion will be considered pre-existing conditions.

Pre-existing conditions, adverse events, and laboratory test results will be graded initially by the site investigator according to Section 8 and entered into eCRFs as specified below and in Section 6.

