(B) Probability of a pregnant woman, who received any amount of RDV for the treatment of COVID-19, having at least one adverse event (maternal Grade 3 or higher/serious/maternal Grade 3 or higher assessed as related by the CMC) through 4 weeks post last infusion and at delivery	 (B) Proportion of participants with at least one adverse event (maternal Grade 3 or higher/serious/maternal Grade 3 or higher assessed as related by the CMC) through 4 weeks post last infusion, bounded by an exact 95% Cl
(C) Probability of a pregnant woman, who received any amount of RDV for the treatment of COVID-19, having at least one labor/delivery outcome (pregnancy loss/congenital anomalies/preterm birth < 37 weeks/preterm birth < 34 weeks/SGA)	(C) Proportion of participants with at least one labor/delivery outcome (pregnancy loss/congenital anomalies/preterm birth < 37 weeks/preterm birth < 34 weeks/SGA), bounded by an exact 95% Cl

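### The labor/delivery proportions in SAP 5.1.2(C) do not require that the outcome was still open at the first RDV infusion; each needs an at-risk row beside the crude one

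*Protocol*

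**What the plan says.** - **Objective.** The safety objective for Arm 1 in the protocol schema reads: "describe the clinical and laboratory safety outcomes through four weeks post-last infusion and during delivery in pregnant women receiving RDV as part of clinical care".
- **Outcomes.** Protocol Table 7 and SAP 3.1 list pregnancy loss, congenital anomalies, preterm birth (<37 and <34 weeks) and SGA as primary labor/delivery outcomes, separate from the adverse-event outcomes. Each is defined by what is found at delivery.
- **Analysis.** SAP 5.1.2(C) uses the "Proportion of participants with at least one labor/delivery outcome" of those types, with an exact 95% CI, in all Arm 1 women who received any RDV. The intercurrent events named are maternal death and terminal fetus/infant events. Nothing is said about conditions already present at the first infusion.
- **Eligibility.** Protocol 4.1.2 requires a "viable intra-uterine pregnancy of any gestational age, based on medical records". Protocol 4.1.3 requires that the woman be "hospitalized AND has confirmed or suspected COVID-19, based on medical records". Sections 4.1 and 4.3 do not exclude a known anomaly, growth restriction, labor or ruptured membranes. The nearest provision is the discretionary 4.3.5, which covers conditions that would "complicate interpretation of study outcome data".
- **Rule for adverse events.** Protocol 7.2 states: "Any untoward medical conditions occurring prior to the first infusion will be considered pre-existing conditions". Table 2 in Protocol 6.3 adds that such conditions are taken as unrelated to RDV.
- **Baseline data.** For Arm 1, the same Table 2 collects "Major obstetrical diagnoses during the current pregnancy prior to start of RDV infusions" and gestational age 48 hours before the first infusion.
- **Stated limitation.** Protocol 9.1 and SAP 2.1 and 5.1.2 warn only that late enrollment may make the results look too favorable.

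**The concern.** The plan handles timing in two ways within one safety objective. A maternal condition present before the first infusion is set aside as pre-existing. An anomaly already seen on a scan, a fetus already growth-restricted and then SGA at birth, or a preterm birth after labor that began before RDV counts in full.

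The preterm outcomes have a second, opposite problem. A woman at or beyond 37 weeks at her first infusion cannot have a birth before 37 weeks, and likewise for 34 weeks, yet she stays in the denominator and lowers the proportion.

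These are the pregnancy-specific primary safety results, from about 20 women, and they are meant for the primary manuscript and the public results posting. One or two women classified differently would change what a reader takes from them. The only bias the documents mention points toward too few events.

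**Working it through.** **Inputs from the documents.** The target is 20 PK-evaluable women per arm with an initial limit of 25 (Protocol 9.4), and the interval is Clopper-Pearson 95% (SAP 5.1.2).

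**Inputs that are assumed.** The documents do not give the number of events *k* that pre-dated RDV, the number *m* of women already past the gestational threshold, or the observed count. They are varied below.

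**1. The plan's own figure.** For x events in n women, the lower limit is the 0.025 quantile of Beta(x, n−x+1) and the upper limit is the 0.975 quantile of Beta(x+1, n−x). For 4/20 this gives 5.7% to 43.7%, matching the printed 6%–44%. All 18 rows of Protocol Table 10 (SAP Table 2) reproduce to the printed whole percent.

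**2. Events that pre-dated RDV.** Remove *k* women from numerator and denominator: (x−k)/(n−k).

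| k | Starting from 4/20 | Starting from 5/25 |
|---|---|---|
| 0 | 20.0% (5.7–43.7) | 20.0% (6.8–40.7) |
| 1 | 3/19 = 15.8% (3.4–39.6) | 4/24 = 16.7% (4.7–37.4) |
| 2 | 2/18 = 11.1% (1.4–34.7) | 3/23 = 13.0% (2.8–33.6) |
| 3 | 1/17 = 5.9% (0.1–28.7) | 2/22 = 9.1% (1.1–29.2) |

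**3. Women past the gestational threshold (preterm birth only).** Remove *m* women from the denominator: x/(n−m), with x = 4 and n = 20.

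| m | Result |
|---|---|
| 3 | 4/17 = 23.5% (6.8–49.9) |
| 5 | 4/15 = 26.7% (7.8–55.1) |
| 8 | 4/12 = 33.3% (9.9–65.1) |

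**4. Both together.** With k = 2 and m = 5, (4−2)/(20−2−5) = 2/13 = 15.4% (1.9–45.4). The two corrections pull in opposite directions, so the sign of the net bias depends on who enrolls.

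**5. Whether this is likely to arise.** If a share q of Arm 1 women have such a condition at the first infusion, the chance of at least one among 20 is 1 − (1−q)^20. For q = 2%, 5% and 10% (assumed), this is 33%, 64% and 88%.

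Pregnancy loss is left out because a viable pregnancy is required at entry.

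**The case against.** **Obstetric admissions.** A reader might infer from 4.1.3 that women admitted for preterm labor or a fetal problem will make up a good part of Arm 1, especially since Protocol 1.1 says of pregnant women's hospitalizations that "these data did not distinguish between hospitalization for COVID-19 conditions from admissions for pregnancy-related indications, such as delivery". That goes too far. The sentence describes national surveillance data. Protocol 3 and 4.5 and SAP 5.1.2 describe women hospitalized for COVID-19 or its treatment, and 4.3.5 lets an investigator exclude a confusing case. Such women can enter under the criteria as written, but nothing shows how many would. The gap does not depend on the reason for admission: a woman hospitalized for COVID-19 can also have a known anomaly or be past 37 weeks.

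**Descriptive aim.** SAP 2.2 states no hypotheses, and delivery outcomes have no comparator in Arm 2. Even an at-risk proportion could not be attributed to RDV. This stands: the crude proportions are not wrong as frequencies, and the point concerns how they are read as safety outcomes.

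**Relatedness review.** Infant anomalies also go on the adverse event log (Protocol 7.2.2), and the CMC confirms relatedness (Protocol 8). This helps interpretation of individual cases. It does not reach 5.1.2(C), and the relatedness-based outcome in SAP 3.1 is limited to maternal events.

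**Coding rules elsewhere.** The Analysis Implementation Plan was not available and may hold a rule, so it cannot be said that the obstetric diagnoses go unused. Still, a condition that changes a primary estimand belongs in the SAP.

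**Trimester display.** SAP 4 presents primary analyses by trimester. This helps partly, but it neither separates earlier diagnoses from new ones nor cuts at 34 or 37 weeks.

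**Conclusion.** The gap is real. The 5.1.2(C) proportions for anomaly, SGA and preterm birth have no at-risk condition, although the protocol applies a before/after rule to adverse events and collects most of what is needed to apply one here.

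At n = 20, one pre-RDV event moves an observed 20.0% by 4.2 points (20.0 − 15.8), and three move it by 14.1 (20.0 − 5.9). Five women past the threshold move it 6.7 points the other way (26.7 − 20.0). All of these rest on assumed counts, and the intervals overlap widely. The gain is correct classification, not precision.

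Two stronger readings are not supported:

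- A reader might infer that the proportions are inflated. The denominator effect runs the other way, so the net direction is not fixed.
- A reader might infer that RDV could not have caused the events in question. Suspected growth restriction or threatened labor before RDV does not settle whether the infant is SGA or born preterm. What can be said is that the process was recorded before exposure.

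**What to change.** Keep the all-treated proportions in SAP 5.1.2(C). Beside each, add a supplementary row among women at risk at the first infusion:

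- **Congenital anomaly and SGA:** no corresponding fetal diagnosis recorded before RDV.
- **Preterm birth, <37 and <34 weeks separately:** gestational age below the threshold at the first infusion, and no labor, membrane rupture or planned preterm delivery recorded before it.

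Use the Table 2 obstetric diagnoses and gestational age, carrying the latter forward two days because it is dated 48 hours before the first infusion. For each row, give the number of women removed and the reason. Add to the stated limitations that delivery outcomes may include events that began before RDV.

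The cost is a paragraph in the SAP and one extra table, using data already abstracted from charts. The added rows have smaller denominators and wider intervals: 4/15 spans 47.3 points (55.1 − 7.8), against 38.0 (43.7 − 5.7) for 4/20. They should therefore stay supplementary.
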